Title: Effects of High Amplitude and Focused tACS on Entraining Physiological Tremor

Date: 01-June-2016

Protocol unfocused electrodes – Healthy volunteers

1. Patient consent (20 min)
 - a. Explain the study
 - b. Let subject read & fill in informed consent
2. Patient preparation (1h)
 - a. Clean big regions of the scalp with ethanol around the left motor cortex and the prefrontal cortex
 - b. Measure Cz, C1 and C3 and place the stimulating electrode between C1 and C3.
 - c. Place another stimulating electrode over the PFC (by measuring F5/F6)
 - d. Place the return electrode over the ankle
 - e. Calibrate the accelerometer
 - f. Place the accelerometer on the middle finger of dominant hand
 - g. Ask subject to adopt a tremor inducing pose
 - h. Measure the tremor frequency for 5 minutes and analyse with specTremor
 - i. Check if impedance is below $5\text{k}\Omega$
 - j. If impedance is too high, add more saline
3. Stimulation amplitude dose response (10 min)
 - a. Instruct the subject to report any stimulation related side effects / secondary effects (tingling, pain, phosphenes)
 - b. Apply stimulation with increasing currents, while
 - i. Monitoring impedance
 - ii. Asking the subject about side effects
 - c. As long as no severe side effects are reported and subject wants to increase the current, increase with small steps (e.g. 0.2 mA) until a maximum of 2mA.
 - d. Repeat for second stimulation site
 - e. Determine the maximal amplitude that is tolerable in both regions. So stimulate the two regions at the same amplitude.
4. Phosphene ratings and thresholds (10 min)
 - a. Check phosphene ratings at maximal stimulation amplitude for both stimulation sites
 - b. If phosphenes are reported, determine the phosphene thresholds for both sites by gradually increasing the stimulation amplitude
5. Stimulation protocol (45 min)
 - a. Measure the tremor frequency
 - b. Perform the stimulation protocol at the maximum stimulation amplitude determined in step 3.
 - c. Record one session of 30 sec OFF-1 min MC-30 sec OFF-1 min PFC repeated 4 times in random order
 - d. Repeat 2 more times to have 3 sessions

Protocol focused electrodes – Healthy volunteers

6. Patient consent (20 min)
 - a. Explain the study
 - b. Let subject read & fill in informed consent
7. Patient preparation (1h)
 - a. Clean big regions of the scalp with ethanol around the left motor cortex and the occipital cortex
 - b. Place the electrode cap over the head of the subject
 - c. Measure if Cz of the cap matches the position of the vertex
 - d. Indicate with marker the position of the stimulating electrodes
 - e. Remove the electrode cap
 - f. Measure if the stimulating electrode is at the correct position (C3). If not, repeat a-e.
 - g. Apply EMLA-cream around the stimulating electrode positions
 - h. Calibrate the accelerometer
 - i. Place the accelerometer on the middle finger of dominant hand
 - j. Ask subject to adopt a tremor inducing pose
 - k. Measure the tremor frequency for 5 minutes and analyse with specTremor
 - l. After half an hour after applying the EMLA cream, check if the hair is dry. If the hair is still too wet, dry with paper/towel or a hairdryer.
 - m. Place the electrode cap over the head of the subject
 - n. Measure the head to ensure that the location of the motor cortex matches the position of the plastic electrode holders.
 - o. Add electrolyte gel inside the electrode holders with a syringe
 - i. 2.5 ml for flat electrode holders
 - ii. 5 ml for Gamma
 - p. Add the electrodes and close the electrode holders
 - q. Check if impedance is below $5\text{k}\Omega$
 - r. If impedance is too high, add more gel or attach rubber straps over the electrodes for good contact of the electrode holders and the scalp.
8. Stimulation amplitude dose response (10 min)
 - a. Instruct the subject to report any stimulation related side effects / secondary effects (tingling, pain, phosphenes)
 - b. Apply stimulation with increasing currents, while
 - i. Monitoring impedance
 - ii. Asking the subject about side effects

- c. As long as no severe side effects are reported and subject wants to increase the current, increase with small steps (e.g. 0.5 mA) until a maximum of 5mA.
- d. Repeat for second stimulation site
- e. Determine the maximal amplitude that is tolerable in both regions. So stimulate the two regions at the same amplitude.

9. Phosphene ratings and thresholds (10 min)

- a. Check phosphene ratings at maximal stimulation amplitude for both stimulation sites
- b. If phosphenes are reported, determine the phosphene thresholds for both sites by gradually increasing the stimulation amplitude

10. Stimulation protocol (45 min)

- a. Measure the tremor frequency
- b. Perform the stimulation protocol at the maximum stimulation amplitude determined in step 3.
- c. Record one session of 1min OFF-1 min MC-1 min OFF-1 min OC repeated 3 times in random order
- d. Repeat 2 more times to have 3 sessions

Statistics

Statistics are performed with a significance level $\alpha=0.05$. A two-sided Wilcoxon signed-rank test compares scores for phosphene intensity and thresholds between the different conditions. For phase entrainment the effect of the condition on the entrainment is tested with a non-parametric Friedman test. If significant, a post-hoc analysis is conducted with a two-sided Wilcoxon Signed-Rank test between all pairs of the conditions. p-values are adjusted for multiple comparisons with a Bonferroni correction.

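### Motor stimulation is fixed on the left but tremor is recorded from the dominant hand, so any left-hander enrolled is measured on the side ipsilateral to stimulation

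*Combined protocol and SAP*

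**What the plan says.** In the unfocused procedure, step 2a prepares the scalp over the left motor cortex ("Clean big regions of the scalp with ethanol around the left motor cortex and the prefrontal cortex") and step 2b sets the electrode position: "Measure Cz, C1 and C3 and place the stimulating electrode between C1 and C3". In the focused procedure, step 7a again names the left motor cortex ("Clean big regions of the scalp with ethanol around the left motor cortex and the occipital cortex") and step 7f verifies it: "Measure if the stimulating electrode is at the correct position (C3). If not, repeat a-e". Neither procedure offers a right-hemisphere alternative.

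The recorded limb is defined differently. Steps 2f and 7i carry the same instruction: "Place the accelerometer on the middle finger of dominant hand".

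The Statistics section says: "For phase entrainment the effect of the condition on the entrainment is tested with a non-parametric Friedman test". If that test is significant, two-sided Wilcoxon signed-rank tests follow on all pairs of conditions, with Bonferroni adjustment. It contains no exclusion, stratification or sensitivity analysis for laterality. The document has no eligibility section and does not mention assessing handedness.

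**The concern.** The side of stimulation is a constant and the side of measurement is a subject characteristic. They are contralateral in right-handers and ipsilateral in left-handers. The entrainment question is whether stimulating the motor cortex affects tremor more than stimulating the control site or not stimulating. That comparison is meaningful only if the recorded hand is the one the stimulated cortex is expected to drive. The focused procedure takes real care over site (checking Cz against the vertex, verifying C3, re-measuring once the cap is back on), and that care is lost for a subject whose other hand carries the accelerometer.

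At stake is the sensitivity of the MC contrasts. For a left-hander, MC behaves in part or in full like a second off-target condition, which weakens both the Friedman test and the post-hoc pairs.

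**Working it through.** **Text comparison**

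| | Unfocused | Focused |
|---|---|---|
| Motor electrode | Left, between C1 and C3 (2a, 2b) | Left, C3 (7a, 7f) |
| Recorded hand | Dominant (2f) | Dominant (7i) |
| Right-hander | Contralateral | Contralateral |
| Left-hander | Ipsilateral | Ipsilateral |

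**Inputs for the illustration.** From the Statistics section: α = 0.05, a Friedman test, then Bonferroni-adjusted signed-rank tests. Everything else is assumed, because the documents give no n, effect size, left-hander share or ipsilateral effect, and there is no power figure to reproduce. Assumptions:

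- three conditions (OFF, MC, control), hence three pairs and a per-pair level of 0.05/3 = 0.0167;
- independent normal values per condition with SD 1/√2, so a paired difference has SD √(1/2 + 1/2) = 1;
- MC mean equal to the effect in right-handers, and to effect × kept share (0 or 0.5) in a left-hander;
- success means Friedman p < 0.05 (chi-square approximation) and exact signed-rank MC versus control below 0.0167.

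**Power, effect 1.0 SD, 40,000 replicates per cell.** The simulation standard error is at most √(0.25/40,000) = 0.0025, a quarter of a point.

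| n | No left-hander | One, none kept | One, half kept | One, dropped (n−1) |
|---|---|---|---|---|
| 10 | 50% | 35% | 43% | 41% |
| 15 | 80% | 70% | 76% | 76% |
| 20 | 93% | 89% | 92% | 92% |

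The loss with none kept is 50 − 35 = 15, 80 − 70 = 10 and 93 − 89 = 4 points. With half kept it is about 7, 4 and 1 points.

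**Other effect sizes, one left-hander, none kept.**

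- 0.8 SD: 30% to 21% at n=10 (9 points); 76% to 69% at n=20 (7 points).
- 1.2 SD: 69% to 50% at n=10 (19 points); 99% to 98% at n=20 (1 point).

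**Under no effect** in any condition, the MC-versus-control rejection rate after the Friedman gate is 0.8 to 1.0%, so there is no inflation.

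**Chance that it arises if handedness is not restricted.** For a left-hander share p:

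- P(at least one) = 1 − (1 − p)^n. At p = 10%, n=10 gives 1 − 0.9^10 = 65%; n=15 gives 79%; n=20 gives 88%. Over p = 5 to 15% and n = 10 to 20 the range is 40% to 96%.
- P(two or more) = 1 − (1 − p)^n − np(1 − p)^(n−1). At p = 10% this is 26%, 45% and 61%.

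**The case against.** The strongest reply is that the defect is conditional on something the document cannot show. It is a short bench procedure with one paragraph of statistics and no eligibility section of any kind, so its silence on handedness is weak evidence that left-handers were admitted. The consent pages are not in the text available for review, and a right-handers rule could stand there. Fixing the left motor cortex and then writing of the dominant hand is also coherent if the authors had only right-handers in mind.

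The harm, moreover, presumes that left-hemisphere stimulation entrains the left hand less than the right, and no passage gives an ipsilateral effect. In the unfocused montage ("Place the return electrode over the ankle") some of the effect may persist, but how much is a guess. The power figures rest on assumptions throughout, and at n=20 the loss is small.

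Most of this stands as a limit on size and certainty. It does not remove the point. The right-handers-only reading is written nowhere in the document, and the steps followed literally give the wrong pairing in a foreseeable kind of subject. If the rule exists elsewhere, stating it here costs a phrase.

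**Conclusion.** The concern holds, in conditional form. As written, any left-hander enrolled is recorded on the hand ipsilateral to the stimulated motor cortex, and the MC contrasts are diluted to the extent that the ipsilateral effect is smaller. Whether any left-hander took part cannot be seen; if none did, the effect is nil.

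The consequence is confined to lost power for entrainment. At an assumed effect of 1.0 SD, one such subject costs roughly 4 to 15 points over n = 20 to 10 in the worst case, and roughly 1 to 7 if half the effect is kept. These figures show the order of magnitude; they are not estimates for this trial. The point should be fixed because the remedy is almost free, but it does not threaten the validity of a positive finding. Confidence is medium, since enrolment, n and the ipsilateral effect are all unknown.

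**What to change.** In steps 2f and 7i, specify the middle finger of the right hand, contralateral to the stimulated left motor cortex, for every subject. Stating right-handedness as an entry criterion resolves the text equally well. Tying the electrode side to the recorded hand would also make the steps consistent, but it changes where stimulation is applied, whereas the first two options do not.

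If left-hand recordings already exist, keep the all-subject Friedman test and post-hoc pairs as primary. Add one sensitivity analysis that leaves those subjects out of the Friedman test and every pair, so that both stages use the same people. Dropping them from the primary analysis is not clearly better: at n=10 with one left-hander it gives 41% power, against 35% (none kept) or 43% (half kept) when the subject is retained.

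The cost is a wording change in two steps or one added criterion. Under the right-hand rule, left-handers are measured on their non-dominant hand; all comparisons are within subject, so this does not bias the contrasts. Under the entry criterion, left-handers cannot take part.

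### Step 10b of the focused protocol takes its amplitude from step 3 (unfocused titration, 2 mA ceiling); it should cite step 8 (focused titration, 5 mA ceiling)

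*Combined protocol and SAP*

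**What the plan says.** The document holds two protocols for healthy volunteers, one with unfocused and one with focused electrodes, under a single run of step numbers. Each goes through consent, preparation, amplitude titration, phosphene assessment and stimulation, in that order. These are steps 1 to 5 in the unfocused protocol and steps 6 to 10 in the focused one.

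- **Unfocused titration (step 3).** Step 3c tells staff to "increase with small steps (e.g. 0.2 mA) until a maximum of 2mA". The two sites, set in steps 2b and 2c, are motor and prefrontal.
- **Focused titration (step 8).** Step 8c tells staff to "increase with small steps (e.g. 0.5 mA) until a maximum of 5mA". The preparation in step 7a names motor and occipital sites: "Clean big regions of the scalp with ethanol around the left motor cortex and the occipital cortex". Step 8e then fixes the amplitude: "Determine the maximal amplitude that is tolerable in both regions. So stimulate the two regions at the same amplitude".
- **Focused recordings (step 10).** Step 10c sets the sequence: "Record one session of 1min OFF-1 min MC-1 min OFF-1 min OC repeated 3 times in random order". Step 10d brings the total to three sessions. Step 10b gives the source of the amplitude: "Perform the stimulation protocol at the maximum stimulation amplitude determined in step 3".

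The step 10b sentence also stands, word for word, as step 5b of the unfocused protocol.

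**The concern.** Step 10b is the instruction that tells the operator where the focused stimulation amplitude comes from, and it points to the other protocol's titration. Taken at its word, it has three consequences.

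1. The focused recordings would run under a 2 mA ceiling although step 8 allows 5 mA.
2. The amplitude would come from a different set-up (ankle return electrode and saline, against a cap with gel-filled holders and EMLA cream) and from a different second site. Step 3 gives no tolerance value for the occipital cortex.
3. A subject who took part only in the focused protocol would have no step 3 value. The focused protocol has its own consent (step 6b: "Let subject read & fill in informed consent"), and nothing says that its subjects also complete steps 1 to 5.

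Amplitude is the dose in this study, and the title puts high amplitude and focused delivery first. The source of the dose should not depend on the operator noticing that a step number is wrong.

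**Working it through.** The plan states no sample size, power or other figure that bears on this point, so there is nothing of that kind to reproduce. The check traces the cross-references and then sizes the gap.

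**Cross-references**

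| | Unfocused protocol | Focused protocol |
|---|---|---|
| Steps | 1–5 | 6–10 |
| Titration step | 3 | 8 |
| Suggested increment | 0.2 mA | 0.5 mA |
| Titration ceiling | 2 mA | 5 mA |
| Sites | motor, prefrontal | motor, occipital |
| Stimulation step | 5 | 10 |
| Amplitude source cited | step 3 (in 5b) | step 3 (in 10b) |
| Source that matches the electrodes and sites | step 3 | step 8 |

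The reference in 5b resolves within its own protocol. The reference in 10b does not. No other text in the document changes the number in 10b.

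**What was meant**

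Titration is the third of five steps in each protocol. Step 8e determines an amplitude for both focused sites and says that they are to be stimulated at it. Step 9 then assesses phosphenes at the maximal amplitude. If 10b really drew on step 3, the step 8 result would play no part in the recordings that follow it. Step 8 is therefore the intended source. The identical wording suggests that the sentence was carried over from 5b, or that the step numbers ran on when the two lists were joined.

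**Size of the gap**

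Literal ceiling over intended ceiling: 2 mA / 5 mA = 0.40. This compares permitted maxima. The document does not report delivered amplitudes.

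**How much stimulation 10b governs**

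One cycle in 10c lasts 1 + 1 + 1 + 1 = 4 min, of which 2 min is stimulation (1 motor, 1 occipital). The total depends on how the repeat instruction is read.

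- Three cycles per session: recording 3 × 3 × 4 = 36 min; stimulation 3 × 3 × 2 = 18 min (9 motor, 9 occipital).
- One cycle plus three repeats: recording 3 × 4 × 4 = 48 min; stimulation 3 × 4 × 2 = 24 min (12 motor, 12 occipital).

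Step 10 is allotted 45 min. Since 36 < 45 < 48, the first reading fits and the second does not. So 10b most likely governs 18 min of stimulation per subject, which is all of the focused recording stimulation.

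**The case against.** The strongest reply is that the slip is harmless because nobody would act on it. Staff would have to titrate the focused electrodes up to 5 mA, settle on an amplitude tolerable at both sites, check phosphenes, and then set all of that aside for a number obtained with other electrodes over a different second site. Step 8e and the title point the other way. Any literal error would lower the ceiling and not raise it. The Statistics section refers to no step number and no amplitude, so no analysis depends on it.

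A second reply is that the running numbers may be an artefact. The focused protocol has its own heading and repeats the same five steps. If its list began again at 1, step 3 would be the right reference.

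Most of this is fair, and it limits the weight of the point. The intent is plain, there is no sign of a wrong dose, and the statistics are untouched. The duration figures show only how much stimulation the instruction covers; they are not a measure of harm. The numbering explanation cannot be excluded from the text alone. If the running numbers are in the source document, however, the reference is wrong for anyone who uses it, whatever the cause. Clear intent makes the correction uncontroversial but does not make the reference right.

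**Conclusion.** The concern holds. With the steps numbered 1 to 10, step 10b cites the wrong titration: step 3, unfocused, motor and prefrontal, up to 2 mA, where step 8, focused, motor and occipital, up to 5 mA, is meant. On a literal reading the focused ceiling falls to 40% of what the plan intends.

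This is a minor correction to an operative instruction. It does not show that any subject received the wrong amplitude. The conclusion assumes that the continuous numbering belongs to the protocol as used. The point about subjects without a step 3 value assumes that some take part in the focused protocol only, which the document neither states nor rules out.

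**What to change.** In step 10b, change step 3 to step 8. Leave step 5b as it is. Restarting the focused list at 1 would also make the reference correct, but would leave two steps with the same number, so the direct edit is cleaner.

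As a precaution, check in the focused session records that the amplitude used was the one found in step 8. The cost is one changed number and a short records check, with no added subjects, visits or procedures.

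### Within a defined family, Holm's step-down correction would give the pairwise tests more power than Bonferroni at the same 5% family-wise level, with no extra data

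*Combined protocol and SAP*

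**What the plan says.** The Statistics section sets alpha at 0.05. On entrainment it says: "For phase entrainment the effect of the condition on the entrainment is tested with a non-parametric Friedman test". It continues: "If significant, a post-hoc analysis is conducted with a two-sided Wilcoxon Signed-Rank test between all pairs of the conditions". It closes: "p-values are adjusted for multiple comparisons with a Bonferroni correction". It gives no reason for choosing Bonferroni and mentions no step-down method.

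The section does not list the conditions that enter each Friedman test. The recording steps suggest three per protocol. Step 5c (unfocused electrodes) reads "Record one session of 30 sec OFF-1 min MC-30 sec OFF-1 min PFC repeated 4 times in random order", and step 10c (focused electrodes) reads "Record one session of 1min OFF-1 min MC-1 min OFF-1 min OC repeated 3 times in random order". That points to OFF, MC and one control site: prefrontal (PFC) in the first protocol, OC in the second.

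The section also plans separate signed-rank tests of phosphene intensity and thresholds. It does not say whether these tests, or the two protocols, share one correction.

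**The concern.** Bonferroni holds every pair to the strictest threshold, even after some pairs have been rejected. Holm relaxes the threshold as rejections accumulate and keeps the same family-wise guarantee, so within a fixed family Bonferroni gives up power for no added protection.

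The design makes this relevant. Each protocol has an active control site as well as OFF periods, so a claim that entrainment is specific to motor-cortex stimulation needs MC to differ from both. That is two pairwise rejections, and the second is where Holm helps. This reading is inferred from the block design; the Statistics section names no key contrast.

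**Working it through.** **Inputs from the documents.** Alpha is 0.05; a Friedman gate is followed by two-sided signed-rank tests of all pairs, with Bonferroni. Three conditions per protocol are inferred from steps 5c and 10c. The plan states no sample size, power or per-pair threshold, so there is no figure of its own to reproduce.

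**Thresholds.** With k = 3 conditions there are 3 × 2 / 2 = 3 pairs.

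- Bonferroni: 0.05/3 = 0.0167 for every pair, and 3 × 0.0167 = 0.05, so the plan holds its alpha.
- Holm: 0.05/3 = 0.0167 for the smallest p-value, 0.05/2 = 0.025 for the next, 0.05/1 = 0.05 for the last, stopping at the first failure.

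The first step is the same, so the chance of at least one rejection is the same. The methods part at the second step: once the smallest p-value has passed, a second one between 0.0167 and 0.025 is significant under Holm only. No Holm threshold is below Bonferroni's, so no Bonferroni rejection can be lost.

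**Smallest usable n.** The smallest exact two-sided signed-rank p-value is 2/2ⁿ. At n = 6 it is 2/64 = 0.031, above 0.0167; at n = 7 it is 2/128 = 0.0156, below it. With three pairs neither method can reject anything below n = 7.

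**Size of the gain (assumed inputs).** Simulation with normal data, paired-difference SD 1, MC shifted by d from both other conditions, Friedman chi-square gate at 0.05, exact signed-rank tests and 20,000 to 40,000 replicates per scenario. Power to show both MC contrasts, Bonferroni to Holm:

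| Scenario | n=10 | n=15 | n=20 |
|---|---|---|---|
| d=0.5 | 4 to 5% | 10 to 12% | 18 to 23% |
| d=0.8 | 17 to 22% | 43 to 49% | 66 to 73% |
| d=1.2 | 56 to 64% | 90 to 93% | 98 to 99% |
| Graded means: OFF 0, control 0.4, MC 1.2 | 29 to 37% | 59 to 68% | 79 to 87% |
| d=0.8, both protocols as one family of six pairs | 8 to 13% | 29 to 39% | 56 to 64% |
| d=0.8, four conditions (six pairs), MC against two named ones | 8 to 13% | 30 to 38% | 55 to 60% |

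At d=1.6 the change is 89 to 93% at n=10 and under half a point from n=15. Repeat runs agree within about one point.

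**Family-wise error within one protocol.** With three conditions and n = 8 to 20, it was 1.3 to 2.6% for the plan and 2.2 to 4.7% for Friedman plus Holm. A larger run (n = 10 to 20, d from 0 to 3.0) gave 1.1 to 2.5% and 1.5 to 5.0%. No replicate of the 20,000-replicate runs had a Bonferroni rejection that Holm missed.

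**Error across both protocols, each corrected separately.** Suppose MC truly differs in both protocols and its effect is large. One true null pair then remains in each. Bonferroni tests it at 0.0167, so the error across two independent protocols is about 1 − (1 − 0.0167)² = 3.3%. Holm can test it at 0.05, giving up to 1 − 0.95² = 9.75%. Simulated ranges with a real MC effect were 2.2 to 3.2% and 2.9 to 9.6%. Under the global null the two methods are identical (4.6 to 5.0%). With one six-pair family, Holm stays at or below 4.6%.

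**The case against.** **Bonferroni is valid and standard, so this is close to a matter of taste.** It is valid, and that is why the point ranks as optional. But Holm's advantage within a fixed family is a mathematical property, and no reason is given for forgoing it.

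**The slack is not wholly needless.** This stands in part. If each protocol has its own family, Bonferroni's slack keeps the error across both protocols under 5% in these scenarios, and Holm uses it up. The equal guarantee holds within the stated family and no further. A sponsor who wants control across both protocols should pool the six pairs.

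**With exactly three conditions, Holm is only a partial remedy.** This also stands. A significant Friedman test followed by unadjusted pairs is then a closed test. Its simulated error was 2.9 to 5.0%, apart from 5.3% at n=6 under the global null, where the chi-square reference is rough. At d=0.8 its power for both MC contrasts was about 35, 62 and 80% at n=10, 15 and 20, well above Holm. But the Statistics section does not state the number of conditions, and the two OFF blocks in each cycle could be pooled or kept apart. With a shift of 0.8 or 1.2 and n = 10 to 20, gate-only error was 9.7 to 12.2% for four conditions and 16.0 to 20.9% for five. Holm is safe for any number.

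**The benefit cannot be sized for this trial.** True: every power figure rests on assumed n and d. The direction does not.

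**Conclusion.** The point holds as a low-priority improvement. The planned correction protects the stated alpha; it is only less powerful than it need be. Holm's superiority within a fixed family needs no assumption about n, effect size, dependence or number of conditions.

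The amount of power does rest on assumptions. With three conditions, normal data and paired-difference SD 1, the gain for showing both MC contrasts is 5 to 7 points at d=0.8 and 8 to 9 points in the graded scenario, for n = 10 to 20. It is small at d=0.5 with n=10 (4 to 5%) and vanishes for large effects. A claim that needs only the smallest p-value gains nothing.

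**What to change.** In the last sentence of the Statistics section, name the Holm step-down correction in place of Bonferroni. Leave the scope of the sentence as it is, so that any adjustment of the phosphene tests is kept, and keep the Friedman gate.

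Add a clause that lists the conditions in each Friedman test and says whether the two protocols are one family or two. The same clause should say whether the phosphene tests are included, since changing the method does not settle that. If control across both protocols is wanted, apply Holm to all their pairs together. Do not rely on the Friedman gate alone while the number of conditions is unstated.

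The cost is a few words and no extra data, and the change should be made before entrainment results are seen. The one statistical price is the higher error across protocols when the families are kept separate, as shown above.
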